**Pre-Drug Arm (up to n=6; enrollment for this Arm will close once 3 men complete their biopsy visit):**

**Visit 1 (screening):** Eligible MSM will provide written informed consent, be questioned about their medical history, undergo a physical exam (conducted by a study clinician) a rapid HIV test, and a peripheral blood sample for a complete blood count, creatinine, coagulation test, and hepatitis B. Participants will then be asked to return within 1- 6 weeks for visit 2.

**Visit 2:** Visit will occur within 1-6 weeks after the screening visit. Approximately 24 mL of blood will be drawn, an oral cheek swab, 1 pre- wet penile swabs and 1 dry penile swab, and a urethral swab will be collected. After previous swab collections are complete, participants will be asked to provide a urine sample, some of which will be used for gonorrhea and chlamydia testing, then the practitioner (Principal investigator or

TITLE OF PROJECT: On-Demand PEP  
Emory IRB  
PRINCIPAL INVESTIGATOR: [name], MPH

Co- investigator) will collect rectal secretion samples by using two swabs and insert an aptima swab for rectal gonorrhea and chlamydia testing, before the participant undergoes a rectal biopsy via rigid sigmoidoscopy.

Participants will be asked to provide an optional single semen sample, which will be collected at home, no more than 2hrs prior to or after the biopsy visit.

After 3 men complete the pre-drug arm, subsequent participants will be sequentially assigned to Arm A, B, C or D.

**Arm A (up to n=16 maximum enrolled):**

**Participants will be sequentially assigned to groups A.1 and A.2. Once 4 men complete their biopsy visits for subgroup A.1, subsequent men will be enrolled into sub-group A.2. A total of 8 men must complete all study visits for this arm.**

**Group A.1 (n=8; enrollment will close once 4 men complete their biopsy visit):**

**Visit 1(screening):** Eligible MSM will provide written informed consent, be questioned about their medical history, undergo a physical exam (conducted by a study clinician) a rapid HIV test, and a peripheral blood sample for a complete blood count, creatinine, coagulation test, and hepatitis B. Participants will then be asked to return within 1- 6 weeks for visit 2.

**Visit 2:** Participants will be given a one- day supply of Genvoya®. Staff will provide instructions to participant on when to take dose at home. Participants will be asked to dose **24hrs before visit 3** and will be instructed to photograph or videotape themselves taking dose with the timestamp included with their smartphone. Study staff will instruct participants to bring the photo/video to their next visit to provide proof of dosing. Participants will also have the option to send a text to a specified number with the time and date of dose if their phone device does not have video/photo capabilities.

**Visit 3:** Visit 3 takes place 24hrs after home dose. During this visit, drugs will be dispensed to participants, and they will be instructed to take one dose of Genvoya®. Men will be dosed on-site (time of dose will be recorded) and asked to return in 2hrs. Procedures should be done as close to 2hrs as possible with a +/- 1 hour window.

**Visit 4:** Visit 4 takes place 2hrs (+/- 1 hour) after on-site dose. Approximately 24 mL of blood will be drawn, an oral cheek swab, 1 pre- wet penile swabs and 1 dry penile swab, and a urethral swab will be collected. After previous swab collections are complete, participants will be asked to provide a urine sample, some of which will be used for gonorrhea and chlamydia testing, then the practitioner (Principal investigator or Co- investigator) will collect rectal secretion samples by using two swabs and insert an

aptima swab for rectal gonorrhea and chlamydia testing, before the participant undergoes a rectal biopsy via rigid sigmoidoscopy.

Participants will be asked to provide an optional single semen sample, which will be collected at home, no more than 2hrs before/after to biopsy visit.

**Visit 5:** Visit 5 takes place 48hrs (+/- 1 hour) after on-site dose. Approximately 24 mL of blood will be drawn, an oral cheek swab, 1 pre- wet penile swabs and 1 dry penile swab, and a urethral swab will be collected. After previous swab collections are complete, participants will be asked to provide a urine sample.

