Participants (up to n=16) enrolled in Arm A will be provided with a single dose of Genvoya®, at study visit 2, and instructed to take the dose at home which they will document with a smartphone photo or video time/date stamp. Participants will return to the clinic 24hrs after taking home dose for visit 3 when participants will be given another single dose of Genvoya. Specimen collection including blood, urine, urethral swab, penile swab, and cheek swab will be collected 2hrs after taking the medication in the clinic (visit 4), and 48hrs after taking the medication in the clinic (visit 5). In addition, participants will be sequentially assigned to undergo rectal swab and biopsy procedure at a single time point, at visit 4 (sub-group A.1) OR visit 5 (sub-group A.2). Participants will also be asked to provide an optional semen specimen within 2hrs of their biopsy procedure to further evaluate drug levels. All participants will undergo only one rectal swab and biopsy procedure.

Participants (up to n=16) enrolled in Arm B will be provided with a single dose of Genvoya®, at study visit 2, and instructed to take the dose at home which they will document with a smartphone photo or video time/date stamp. Participants will return to the clinic 24hrs after taking home dose for visit 3 when participants will be given another single dose of Genvoya. Specimen collection including blood, urine, urethral swab, penile swab, and cheek swab will be collected 4 hours after taking the medication in the clinic (visit 4), and 72hrs after taking the medication in the clinic (visit 5). In addition,

TITLE OF PROJECT: On-Demand PEP  
Emory IRB  
PRINCIPAL INVESTIGATOR: [name], MPH

participants will be sequentially assigned to undergo rectal swab and biopsy procedure at a single time point, at visit 4 (sub-group B.1) OR visit 5 (sub-group B.2). Participants will also be asked to provide an optional semen specimen within 2hrs of their biopsy procedure to further evaluate drug levels. All participants will undergo only one rectal swab and biopsy procedure.

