**Group B.1 (n=8; enrollment will close once 4 men complete their biopsy visit):**

**Visit 1(screening):** Eligible MSM will provide written informed consent, be questioned about their medical history, undergo a physical exam (conducted by a study clinician) a rapid HIV test, and a peripheral blood sample for a complete blood count, creatinine, coagulation test, and hepatitis B. Participants will then be asked to return within 1- 6 weeks for visit 2.

**Visit 2:** Participants will be given a one- day supply of Genvoya®. Staff will provide instructions to participant on when to take dose at home. Participants will be asked to dose **24hrs before visit 3** and will be instructed to videotape or photograph themselves taking dose with the timestamp included. Study staff will instruct participants to bring the video/photo to their next visit to provide proof of dosing. Participants will also have the option to send a text to a specified number with the time and date of dose if their phone device does not have video capabilities.

**Visit 3:** Visit 3 takes place 24hrs after home dose. During this visit, drugs will be dispensed to participants, and they will be instructed to take one dose of Genvoya®. Men will be dosed on-site (time of dose will be recorded) and asked to return in 4hrs. Procedures should be done as close to 4hrs as possible with a +/- 1 hour window.

**Visit 4:** Visit 4 takes place 4hrs (+/- 1 hour) after on-site dose. Approximately 24 mL of blood will be drawn, an oral cheek swab, 1 pre- wet penile swabs and 1 dry penile swab, and a urethral swab will be collected. After previous swab collections are complete, participants will be asked to provide a urine sample, some of which will be used for gonorrhea and chlamydia testing, then the practitioner (Principal investigator or Co- investigator) will collect rectal secretion samples by using two swabs and insert an aptima swab for rectal gonorrhea and chlamydia testing, before the participant undergoes a rectal biopsy via rigid sigmoidoscopy.

Participants will be asked to provide an optional single semen sample, which will be collected at home, no more than 2hrs before/after the biopsy visit.

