**Arm D (n=8; enrollment will close once 4 men complete their biopsy visit):**

**Visit 1 (screening):** Eligible MSM will provide written informed consent, be questioned about their medical history, undergo a physical exam (conducted by a study clinician) a rapid HIV test, and a peripheral blood sample for a complete blood count, creatinine, coagulation test, and hepatitis B. Participants will then be asked to return within 1- 6 weeks for visit 2.

**Visit 2:** Participants will be given a one- day supply of Genvoya®. Staff will provide instructions to participant on when to take dose at home. Participants will be asked to dose **24hrs before visit 3** and will be instructed to videotape or photograph themselves taking dose with the timestamp included. Study staff will instruct participants to bring the video/photo to their next visit to provide proof of dosing. Participants will also have the option to send a text to a specified number with the time and date of dose if their phone device does not have video capabilities.

**Visit 3:** Visit 3 takes place 24hrs after home dose. During this visit, drugs will be dispensed to participants, and they will be instructed to take one dose of Genvoya®. Men will be dosed on-site (time of dose will be recorded) and asked to return in 8hrs. Procedures should be done as close to 8hrs as possible with a +/- 1 hour window.

**Visit 4:** Visit 4 takes place 8hrs (+/- 1 hour) after on-site dose. Approximately 24 mL of blood will be drawn, an oral cheek swab, 1 pre- wet penile swabs and 1 dry penile swab, and a urethral swab will be collected. After previous swab collections are complete, participants will be asked to provide a urine sample, some of which will be used for gonorrhea and chlamydia testing, then the practitioner (Principal investigator or Co- investigator) will collect rectal secretion samples by using two swabs and insert an aptima swab for rectal gonorrhea and chlamydia testing, before the participant undergoes a rectal biopsy via rigid sigmoidoscopy.

Participants will be asked to provide an optional single semen sample, which will be collected at home, no more than 2hrs before/after the biopsy visit.

All participants will be asked to abstain from receptive anal intercourse for three days prior to drug dosing and during the study protocol in order to limit additional exposures (e.g. semen, douching, additional lubricants) to the rectal mucosa.

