All participants who will undergo a rectal biopsy will be informed not to place anything into the rectum and abstain from intercourse 7 days after their rectal biopsy procedure to allow the mucosa to heal. If tested positive for gonorrhea and/or chlamydia, participant will be notified and referred to linkage for treatment.

*Biologic specimens:*

TITLE OF PROJECT: On-Demand PEP  
Emory IRB  
PRINCIPAL INVESTIGATOR: [name], MPH

Biologic specimens collected after the screening visit will be transferred directly to CDC for measurement of study drug levels. Specimens will be labeled with a unique ID that only the Emory study team will be able to link to identifiable information. CDC personnel will not have access to identifiable information.

*Contingency visit:*

Attempts to ensure adherence to the study visits will be made with telephone and/or email reminders to the participant. However, if for example, screening laboratory results are lost or are inconclusive or if a participant has been unable to adhere to study protocol, he may be rescheduled for a future date where the above visit procedures will be performed. These additional visits will be scheduled within the above visit windows.

*Timing of procedures after dose:*

The procedures conducted after dose, particularly those less than 24 hours after dose, should occur as close to the scheduled time points as possible. Protocol deviations will be filed for visits that occur outside of the target windows identified above only if the visit is conducted more than 3 hours beyond the target window defined above for each arm and visit.

*Phone calls/retention contacts:*

While on study, periodic phone calls, texts, or email reminders will occur between study staff and participants to ensure proper retention and adherence to study protocol.

Rectal biopsy procedures

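### Early urine in Arms A and B: no bladder emptying at the second dose and no last-void time is mentioned, so up to 16 of 52 post-dose specimens may contain an unknown share of pre-dose urine

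*Combined protocol and SAP*

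**What the plan says.** At visit 3 the man receives his second dose in the clinic, 24 h after the first. For Arm A the text reads "Men will be dosed on-site (time of dose will be recorded) and asked to return in 2hrs", and for Arm B "Men will be dosed on-site (time of dose will be recorded) and asked to return in 4hrs". Visit 3 contains dispensing, dosing, the recorded dose time and the return time, and nothing on voiding.

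Visit 4 follows: "Visit 4 takes place 2hrs (+/- 1 hour) after on-site dose" in Arm A and "Visit 4 takes place 4hrs (+/- 1 hour) after on-site dose" in Arm B. After blood and swabs, the instruction on urine is "After previous swab collections are complete, participants will be asked to provide a urine sample". The same wording is used in A.2, B.1, B.2 and Arm D. In A.1, B.1 and D part of this urine also goes to gonorrhea and chlamydia testing.

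The paragraph on timing of procedures after dose and the specimen table under Figure 1 add no void at dosing, last-void time or urine volume.

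The Lay Summary includes urine in the Arm A list that ends "cheek swab will be collected 2hrs after taking the medication in the clinic (visit 4", with parallel statements for the other arms. It then says that the four drugs will be measured in the specimens and that results will be compared between arms, which here largely means between time points.

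**The concern.** Blood drawn 2 h after a dose reflects the level at 2 h. A urine specimen passed at 2 h reflects the whole period since the bladder was last emptied. If that was before the on-site dose, the specimen combines urine formed late in the first dosing interval with urine formed after the second dose. If the man voided between dosing and visit 4, it contains post-dose urine only, over a shorter and unstated interval. Both specimens carry the same nominal time.

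The protocol records the dose time, which fixes the clock for blood, swabs and tissue. For urine a second time is needed, that of the last void, and the protocol does not mention it.

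What is at stake is the early part of the urine profile, with 8 planned completers at each of 2 h and 4 h. For a given void interval, mixing is greater at 2 h than at 4 h, so it can alter the apparent rise as well as add scatter. At 24 h and later it would need a man not to have voided for a day.

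**Working it through.** The documents give no figure for urine flow, void times or volume, so there is no stated figure to reproduce.

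**Number of specimens.** Arms A, B and C each require 8 men to complete all visits, with urine at visits 4 and 5. Arm D closes at 4 completed biopsy visits, with urine at visit 4 only.

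- Post-dose urine specimens: 3 × 8 × 2 + 4 = 52.
- At 2 h (Arm A, visit 4): 8. At 4 h (Arm B, visit 4): 8. Together 16.

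Sixteen is a ceiling. It is reached only if no man in either arm empties his bladder at the dose or between the dose and visit 4.

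**Pre-dose share of volume.** Let v be the hours from last void to dose (assumed, 0.5 to 3 h) and t the hours from dose to collection (protocol). With steady flow and no void in between, f = v/(v + t).

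| t | v = 0.5 h | v = 1 h | v = 2 h | v = 3 h |
|---|---|---|---|---|
| 2 h | 20% | 33% | 50% | 60% |
| 4 h | 11% | 20% | 33% | 43% |
| 8 h (Arm D) | 6% | 11% | 20% | 27% |

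If the man voided after dosing, f = 0 (ignoring residual volume).

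**Sensitivity to the visit window.** Over the same v, the ±1 h window gives:

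- Arm A: 33–75% at 1 h and 14–50% at 3 h.
- Arm B: 14–50% at 3 h and 9–38% at 5 h.

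Deviations are filed "only if the visit is conducted more than 3 hours beyond the target window defined above for each arm and visit", so a nominal 2 h visit could run to 2 + 1 + 3 = 6 h unflagged, where f is 0.5/6.5 = 8% to 3/9 = 33%. That tolerance affects every specimen type and is a separate matter.

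**Sensitivity to flow.** If post-dose flow is k times pre-dose flow, f = v/(v + kt).

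- k = 2: 11–43% at 2 h, 6–27% at 4 h.
- k = 0.5: 33–75% at 2 h, 20–60% at 4 h.

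**From volume to concentration.** The measured level is f × C_pre + (1 − f) × C_post. With r = C_pre/C_post, it is 1 − f(1 − r) of the post-dose level. The documents give no r, so these values are illustrative:

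| r (assumed) | 2 h, f = 0.20 to 0.60 | 4 h, f = 0.11 to 0.43 |
|---|---|---|
| 0.1 | 82% to 46% | 90% to 61% |
| 0.5 | 90% to 70% | 94% to 79% |
| 1 | 100% | 100% |

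Pre-dose urine carries drug from the first dose, so mixing pulls the reading toward the level about 24 h after dose 1, not toward zero.

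**The case against.** The best reply is that urine is peripheral. The objective under Figure 1 concerns mucosal tissues, and the stated goal is pharmacokinetics and tissue distribution. No urine endpoint, excretion estimate or urine-specific comparison is defined. This stands, and it keeps the point minor. Urine is nevertheless collected at every specimen visit, and the statement on drug assays excepts no specimen type.

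A second reply is that the Lay Summary gives a collection time and never calls the urine result an instantaneous level. That is also fair. A timed void would not produce an instantaneous level either; it would give an average over 0–2 h or 0–4 h after the second dose. The gain is a known interval that is the same in kind for every man.

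Third, the men are told to return later, so some will void in between, especially by 4 h. This is correct, and it is why the count must read up to 16.

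Fourth, emptying the bladder at dosing may leave less urine at visit 4, where the window opens at 1 h in Arm A and part of the specimen in A.1 and B.1 is needed for STI testing. This is a real cost and is carried into the fix.

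A reader might go further and infer three things that the documents do not support:

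- **That early urine levels are biased by 20–60%.** Those figures are volume shares under assumed void times. The change in concentration needs r as well.
- **That void times go unrecorded.** CRFs are mentioned under Subject Privacy and Data Confidentiality but are not among the documents. One can say only that the protocol does not mention a void time.
- **That Arm D is equally affected.** Its wording is the same ("Visit 4 takes place 8hrs (+/- 1 hour) after on-site dose"), but the shares are smaller and 8 h without a void is unlikely.

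**Conclusion.** The point holds as a minor, inexpensive improvement. As written, the protocol allows the 2 h and 4 h urine specimens in Arms A and B to contain pre-dose urine in a proportion that differs between men. Unless a form outside the documents captures the last void, analysis cannot identify or correct it.

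Up to 16 of 52 post-dose urine specimens may be involved. The volume shares of 20–60% at 2 h and 11–43% at 4 h rest on three assumptions that are not in the documents: a last void 0.5–3 h before the dose, steady flow, and no void before visit 4. The size of any shift in concentration is not established. Blood, swabs and tissue are not affected.

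**What to change.** 1. At visit 3 in Arms A and B, add: *Ask the participant to empty his bladder at the time of the on-site dose.* The same line in Arm D is optional.
2. Add one CRF field to every urine collection: *Time of last void before this specimen.* This also covers men who void between dosing and visit 4.
3. State that early urine levels will be reported by collection interval (last void to collection, relative to the second dose) rather than as a 2 h or 4 h level. Flag any specimen whose last void preceded the on-site dose.

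With the bladder emptied at the dose, v = 0 and the pre-dose share falls to zero, ignoring residual volume.

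The cost is one instruction and one CRF field, with no extra visit or specimen. The drawback is a possibly smaller volume at visit 4, so the protocol should say which use of the urine takes priority in A.1 and B.1 if there is too little for both drug levels and STI testing. If a void at dosing is judged impractical, recording the last void alone would still show which early specimens can contain pre-dose urine.

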**Group A.2 (up to n=8; enrollment will close once 4 men complete their biopsy visit):**

**Visit 1(screening):** Eligible MSM will provide written informed consent, be questioned about their medical history, undergo a physical exam (conducted by a study clinician) a rapid HIV test, and a peripheral blood sample for a complete blood count, creatinine, coagulation test, and hepatitis B. Participants will then be asked to return within 1- 6 weeks for visit 2.

**Visit 2:** Participants will be given a one- day supply of Genvoya®. Staff will provide instructions to participant on when to take dose at home. Participants will be asked to dose **24hrs before visit 3** and will be instructed to videotape or photograph themselves taking dose with the timestamp included. Study staff will instruct participants to bring the video/photo to their next visit to provide proof of dosing. Participants will also have the option to send a text to a specified number with the time and date of dose if their phone device does not have video capabilities.

**Visit 3:** Visit 3 takes place 24hrs after home dose. During this visit, drugs will be dispensed to participants, and they will be instructed to take one dose of Genvoya®. Men will be dosed on-site (time of dose will be recorded) and asked to return in 2hrs. Procedures should be done as close to 2hrs as possible with a +/- 1 hour window.

**Visit 4:** Visit 4 takes place 2hrs (+/- 1 hour) after on-site dose. Approximately 24 mL of blood will be drawn, an oral cheek swab, 1 pre- wet penile swabs and 1 dry penile swab, and a urethral swab will be collected. After previous swab collections are complete, participants will be asked to provide a urine sample.

**Visit 5:** Visit 5 takes place 48hrs (+/- 1 hour) after on-site dose. Approximately 24 mL of blood will be drawn, an oral cheek swab, 1 pre- wet penile swabs and 1 dry penile swab, and a urethral swab will be collected. After previous swab collections are complete, participants will be asked to provide a urine sample, some of which will be

TITLE OF PROJECT: On-Demand PEP  
Emory IRB  
PRINCIPAL INVESTIGATOR: [name], MPH

used for gonorrhea and chlamydia testing, then the practitioner (Principal investigator or Co- investigator) will collect rectal secretion samples by using two swabs and insert an aptima swab for rectal gonorrhea and chlamydia testing, before the participant undergoes a rectal biopsy via rigid sigmoidoscopy.

Participants will be asked to provide an optional single semen sample, which will be collected at home, no more than 2hrs before/after the biopsy visit.

